## 8.4 DESIGN: Briefly describe the study design (e.g., observational, interventional, randomized, placebo-controlled, blinded, cross-over, cross-sectional, longitudinal, pharmacokinetic, etc.):

We will recruit 640 rural dementia caregiver adults through 19 community organizations (serving rural communities in 17 states to implement a randomized, attention controlled clinical trial. Caregivers will be randomized to receive the online intervention (workshop) group or attention control group. The online workshops will be facilitated by trained caregivers who will lead workshops. We will assess both primary and secondary outcomes at baseline, 1.5 months (post intervention), 6 and 12 months, with the main intervention group comparison being at 12 months. Interested control group caregivers also will be offered the workshop after the trial is completed.

Using mixed methods approach we will identify implementation characteristics pertinent to caregivers, identify patterns of experience across all workshop participants via analysis of implementation questions embedded in trial surveys administered to all participants. To more deeply understand these experiences, we will interview a sample of 60 caregivers—15 per US region (West, Midwest, Northeast, South).

To determine implementation characteristics pertinent to community organizations, we will collect data from our partner community organizations on experiences of barriers and facilitators. Analyses will compare and contrast characteristics within and between organizations. Findings will

identify essential elements of workshop implementation that should be incorporated into future implementation efforts. Findings on effective and ineffective strategies will inform the implementation of other online programs for rural, caregiver, and Alzheimer's disease populations.

**8.5 BACKGROUND AND SIGNIFICANCE: Briefly provide the background and significance of this study (e.g. why is this study needed) (space limit: one half page):**

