**8.26 STATISTICAL METHODS: Briefly summarize the methods and types of analyses that will be performed:**

**Aim 1 Data Analysis Methods.**

**Descriptive analyses.** Caregiver and caregiver-reported partner socio-demographic characteristics, chronic conditions, and health utilization outcomes will be summarized as means ( $\pm$ SD), frequencies, percentages, and 95% confidence intervals at baseline and 1.5, 6, and 12 months. The distributions of covariates at baseline will be checked for balance between the two groups with histograms and/or boxplots.

**Primary analyses.** Primary analyses will compare caregiver stress (stress score) and depression symptoms (PHQ-8 score) between intervention and control groups over time with respective linear mixed effects models. Linear mixed effects models use all available observations in the data, assume data are missing at random, and provide an intention-to-treat analysis. Models will include group, time, and (group\*time) interaction terms as fixed effects and community organizations and subjects as random effects to account for the correlation within organizations and subjects due to measurements over time. Covariates with imbalanced distributions between the two groups will also be included in the models to control for potential confounding. The (group\*time) interaction term will be used to evaluate if the two groups differ in outcomes over time. The study is powered to allow 30% loss to follow up. To assess for potential differential withdrawal between groups, comparisons of withdrawal rates and time to withdrawal will be performed. Models based on a potential outcome framework will be used to assess treatment effect while accounting for noncompliance and missing data and to examine potential treatment mechanisms/pathways via intermediate variables (such as social support, self-efficacy, caregiving skills). Multiple imputation based on reasonable assumptions on mechanisms of missing data will be used to perform sensitivity analyses.

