## 10.0 Sample Size and Eligibility Criteria

**10.1 ENROLLMENT TARGET: How many people will you enroll:**

If there are multiple participant groups, indicate how many people will be in each group:

**For Aim 1 Sample for RCT.** We will recruit 640 rural dementia caregiver adults through 19 community organizations (serving rural communities in 17 states to implement a randomized, attention controlled clinical trial. 320 in the intervention group and 320 in the control group for a total of n=640.

**For Aim 2 Sample for In-depth Interviews.** We will randomly select a sub-set of intervention group caregivers for semi-structured telephone interviews regarding workshop implementation characteristics. We will sample for caregivers (n=60 total) from all US regions (n=15 per region—West, Midwest, South, Northeast).

**For Aim 1 and Aim 2 Sample for Learning Collaborative.** 19 community organizations (serving rural communities in 17 states) will have at most 2 representatives participating in the Learning Collaborative (n=2\*19=38).

**10.3 SAMPLE SIZE JUSTIFICATION: Explain how and why the number of people was chosen. For multi-site studies, this is referring to the number that will be enrolled across all sites:**

The study is powered on the co-primary outcome with the lowest effect size in pilot studies—the PHQ-8 depression symptoms score (effect size 0.27). We will use a recruitment target of 640 participants. We assume 30% loss to follow-up, thus expecting 448 caregivers (224 per group) will complete the study at 12 months. This sample size of 448 will allow us to detect a PHQ-8 effect size of 0.265 with a power of 0.8 at a significance level of 0.05 (two-sided). The effect size of 0.265 corresponds to a 1.5 difference in PHQ-8 score (range 0-24) between groups assuming a common standard deviation of 5.6. We also will have the power to detect a 1.4 difference in the co-primary outcome of stress score (range 0-10) between the two groups.

If we encounter problems meeting trial enrollment benchmarks, we will work with local organizations and others to find alternative recruitment strategies such as health system-based patient portals or recruitment through national caregiver discussion groups. We also can add additional partner organizations after the start of the study.

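### The within-subject covariance is left to a subject random effect; read as a random intercept, it understates the error of the 0-to-12-month group-by-time contrast or slope if correlation fades

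*Combined protocol and SAP*

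**What the plan says.** Section 8.26 (Aim 1, primary analyses) of the combined protocol and SAP fits a linear mixed model to each co-primary outcome, stress and PHQ-8. The fixed effects are group, time and their interaction. The only stated provision for repeated measures is to enter "community organizations and subjects as random effects to account for the correlation within organizations and subjects due to measurements over time".

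For the test, the plan says that the group-by-time "interaction term will be used to evaluate if the two groups differ in outcomes over time". It does not say whether time is categorical or linear, nor whether the test is joint over follow-up visits or a single contrast.

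Section 8.4 schedules assessments "at baseline, 1.5 months (post intervention), 6 and 12 months", "with the main intervention group comparison being at 12 months". Section 8.26 relies on missingness at random, and section 10.3 allows 30% loss to follow-up. Neither document gives a within-subject correlation.

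**The concern.** A single random intercept per subject implies the same correlation between visits 1.5 months apart as between visits 12 months apart. The visits are unequally spaced, and the 0-to-12-month contrast spans the longest gap. If correlation declines with the gap, the model averages in the higher short-gap correlations and so assumes too little variance for exactly that contrast. A linear slope, which gives most weight to the two ends, suffers more.

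The group-by-time interaction is the plan's named test for both co-primary outcomes, and section 8.26 carries similar models over to the secondary outcomes. What is at stake is the type I error rate of that test. Because the covariance, the coding of time and the contrast are all open, the error rate could lie close to nominal or above 10%, depending on choices not yet fixed.

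**Working it through.** **The plan's own figure.** Section 10.3 gives effect size 0.265, 224 completers per group and two-sided alpha 0.05. Power = Φ(0.265 × √(224/2) − 1.96) = Φ(2.805 − 1.96) = 0.80. This reproduces. The formula contains no within-subject correlation, so the present point does not touch it.

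**Inputs.** From the documents: visits at 0, 1.5, 6 and 12 months; SD 5.6; 320 per group; 30% loss. The Protocol document (the power memo) later adopts varying allocation ratios, but the ratio does not alter the mechanism. Assumed: equal variance at each visit, no organization effect, and correlation falling linearly with the gap g,

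ρ(g) = 0.75 − (0.75 − r)(g − 1.5)/10.5,

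where r is the baseline-to-12-month correlation. The six gaps are 1.5, 6, 12, 4.5, 10.5 and 6 months, with mean 40.5/6 = 6.75. The mean correlation is therefore ρ̄ = 0.75 − (0.75 − r) × 5.25/10.5 = (0.75 + r)/2.

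**0-to-12-month contrast, complete data.** The true variance of a subject's change is 2σ²(1 − r). The random-intercept model uses 2σ²(1 − ρ̄). The ratio of reported to true SE is √[(1 − ρ̄)/(1 − r)], and the actual two-sided error is 2[1 − Φ(1.96 × ratio)].

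| r | ρ̄ | SE ratio | Actual error |
|---|---|---|---|
| 0.75 (flat) | 0.75 | 1.00 | 5.0% |
| 0.65 | 0.70 | √(0.30/0.35) = 0.93 | 7.0% |
| 0.55 | 0.65 | √(0.35/0.45) = 0.88 | 8.4% |
| 0.45 | 0.60 | √(0.40/0.55) = 0.85 | 9.5% |

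**Linear group-by-time slope, complete data.** The centred times are c = (−4.875, −3.375, 1.125, 7.125), with Σc² = 87.19. In units of σ², the model's variance is (1 − ρ̄)Σc² and the true variance is c′Rc, where R is the correlation matrix.

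| r | Model | True | SE ratio | Actual error |
|---|---|---|---|---|
| 0.65 | 26.16 | 32.87 | 0.89 | 8.0% |
| 0.55 | 30.52 | 43.94 | 0.83 | 10.2% |
| 0.45 | 34.88 | 55.00 | 0.80 | 11.9% |

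**With 30% loss** (10% before each follow-up visit, completely at random). The limiting random-intercept fit was found by maximum likelihood and its SE compared with the sandwich SE. For the contrast the ratios are 0.92, 0.87 and 0.84, with errors of about 7.2%, 8.7% and 9.9%. For the slope they are almost unchanged.

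**Wider set of patterns.** These run from a mild decline (0.70 to 0.60) to exponential decay reaching 0.5 or 0.3 at 12 months. Across them the contrast's SE ratio runs from 0.94 to 0.76 (error about 7% to 14%) and the slope's from 0.91 to 0.70 (about 8% to 17%).

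**Tests that are little affected.**
- Joint 3-df interaction test: 5.1% to 5.8% under the three linear patterns with complete data, and 5.1% to 8.0% over the wider set, with and without loss.
- Group difference at 12 months from the same categorical-time model: SE ratio 1.00 with complete data, because it depends only on the total variance at that visit; 0.99 to 0.95 with 30% loss (error at most 6.3%).

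**If the subject effect included a random slope**, the SE ratio would be 1.00 to 1.04, and the understatement disappears.

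**The case against.** The strongest reply is that the text does not say intercept only. Section 8.26 asks for a brief summary, and naming subjects as random effects excludes neither a random slope nor a residual structure. That stands: a reader might infer that the plan forces equal correlation, and the documents do not support so strong a statement. What they show is a covariance that is not pre-specified, whose plain reading is the vulnerable one.

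The second reply is that section 8.4 puts the main comparison at 12 months, and the SE of the between-group difference there is nearly right even under a random intercept. That also stands. A reader might infer that any 12-month standard error is too small; the understatement lies in change from baseline and in the slope. Likewise, if time is categorical and the interaction is tested jointly, the error is mild. But section 8.26 names the interaction as its test without settling its form, so these replies show which choices would be safe, not that the plan has made them.

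Third, harm is conditional. The documents give no correlation, and fading is an assumption about these outcomes. It cannot be said that the p-values for both primary outcomes will be anticonservative, only that they would be under fading correlation with the exposed tests.

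The multiple imputation and potential-outcome models in section 8.26 do not answer the point. They address missing data and noncompliance, not the covariance.

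**Conclusion.** The concern holds as a conditional point about an under-specified model. Three conditions are needed: the subject effect is an intercept only, correlation fades with time, and the test is the 0-to-12-month contrast or a linear slope. Under the linear patterns from 0.75 to 0.65–0.45, the actual error of a nominal 5% test is then about 7% to 9.5% for the contrast and 8% to 12% for the slope; steeper decay gives more, and flat correlation gives none. The joint test is mildly affected, and the 12-month group difference hardly at all.

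A reader might also infer that the study's stated power is wrong. It is not: 0.80 reproduces and does not depend on this choice. The case for a change is that a clearly safer specification is available at almost no cost.

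**What to change.** In section 8.26, state that:

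1. Time is categorical (four visits).
2. An unstructured within-subject covariance over the four visits replaces the subject random intercept, and the organization random effect is kept.
3. Kenward-Roger degrees of freedom are used.
4. The 12-month contrast is the primary test, written out explicitly, in line with section 8.4.
5. If the model does not converge, the first fallback is a subject random intercept and slope, or another structure that lets correlation fade. The last is a random intercept with robust standard errors.

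The order in item 5 matters. Robust standard errors repair the SE only. When data are missing at random rather than completely at random, a misspecified covariance can also bias the estimate, and robust errors do not remove that.

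The cost is a few sentences. Four variances and six covariances make ten parameters, which is trivial with about 640 participants, and almost nothing is lost if correlation is in fact flat. If the contrast chosen is change from baseline, its power depends on the correlation. For 0.265 × 5.6 = 1.484 points, with 320 per group and 30% loss, it is about 0.91, 0.84, 0.78 and 0.72 for baseline-to-12-month correlations of 0.6, 0.5, 0.4 and 0.3 (all assumed). Any higher figure from a random-intercept model under fading correlation would reflect only its understated SE.

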If enough caregivers are enrolled in a 2-week period (e.g., 54) to use a 1:1 randomization, that will be used; if there are somewhat fewer (e.g., 41), 2:1 randomization will be used; if fewer (e.g., 36), 3:1 randomization will be used. Use of this flexible approach has achieved high retention rates in the prior trials (e.g., Lorig KR, Sobel DS, Stewart AL, et al. Evidence suggesting that a chronic disease self-management program can improve health status while reducing hospitalization: a randomized trial. *Medical care* 1999;37:5-14). Assuming that the

randomization with varied ratios will increase the retention rate from 50% to 75% and the randomization ratio will be controlled for as a categorical variable in the analysis model, 480 caregivers at the end of the study will allow us to detect a partial correlation of 0.13 between the treatment and outcome with a power of 0.82 at a significance level of 0.05 (two-sided).

Randomization plan	Total sample size	Retention rate	# participants at the end of the study	Power	Effect size
Original 1:1	640	70%	448	0.80	0.265 (a treatment group difference of 1.5 in PHQ-8 score)
Original 1:1 but with revised downward estimate of retention based on new information from VA	640	50%	320	0.63	0.265
Fixed 2:1	640	75%	480	0.78	0.265
Fixed 3:1	640	75%	480	0.71	0.265
Varying 1:1, 2:1, 3:1	640	75%	480	0.82	A partial correlation of 0.13 between treatment and PHQ-8 score.

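### Primary-model covariates are chosen by eye on baseline imbalance, so the model is not fixed in advance and omits the randomisation ratio that the power memo promises

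*Combined protocol and SAP*

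**What the plan says.** **Combined protocol and SAP, section 8.26, Aim 1.** The descriptive paragraph sets up the check: "The distributions of covariates at baseline will be checked for balance between the two groups with histograms and/or boxplots". The primary-analysis paragraph acts on it: "Covariates with imbalanced distributions between the two groups will also be included in the models to control for potential confounding". Neither paragraph lists candidate covariates, gives a cut-off, or says whether a covariate enters as a main effect or also by time. Neither requires the choice to be made before outcomes are seen.

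The model is a linear mixed model with "community organizations and subjects as random effects to account for the correlation within organizations and subjects due to measurements over time". The test is the group-by-time term: the "interaction term will be used to evaluate if the two groups differ in outcomes over time". Section 8.4 gives the visits as "baseline, 1.5 months (post intervention), 6 and 12 months, with the main intervention group comparison being at 12 months", so baseline is one of the repeated outcomes.

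**Protocol (power memo of August 2019), part on the varying randomisation ratio.** Here one covariate is fixed whatever the balance: "the randomization ratio will be controlled for as a categorical variable in the analysis model". Section 8.26 does not mention it.

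**The concern.** A rule that selects on observed imbalance has three weaknesses.

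- **The model is open.** Two competent analysts looking at the same boxplots could fit different primary models. With no threshold and no timing rule, nothing in the plan prevents the choice from being made after both results are known.
- **It selects on the wrong property.** In a randomised trial, the error rate of the test already allows for chance imbalance. Adjustment earns precision when a covariate predicts outcome, and an imbalance check does not look at that.
- **It leaves the ratio to chance.** Under the memo's 1:1, 2:1 or 3:1 scheme, the probability of assignment to the workshop differs between two-week recruitment periods. Ratio is therefore linked to arm by design. Whether it enters the model should not depend on how a plot looks.

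At stake are a fixed primary analysis, possible bias if recruitment periods differ in outcome, and, in some versions of the analysis, a few points of power.

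**Working it through.** **1. The plan's own figure.** Section 10.3 states: "This sample size of 448 will allow us to detect a PHQ-8 effect size of 0.265 with a power of 0.8 at a significance level", and that this effect "corresponds to a 1.5 difference in PHQ-8 score (range 0-24) between groups assuming a common standard deviation of 5.6". With 224 per arm:

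- power = Φ(d·√(n/2) − 1.96) = Φ(0.265 × √112 − 1.96) = Φ(2.804 − 1.96) = Φ(0.844) = 0.80 (0.801 unrounded)

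The figure reproduces. It is an unadjusted calculation, so it takes no credit for covariates and the selection rule cannot push power below it.

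**2. The group-by-time test, covariates as main effects.** Simulation of a random-intercept model with 4 visits, 320 per arm, intraclass correlation 0.5, the organisation effect omitted, and 2,000 runs per setting. The correlation ρ between covariate and outcome, the intraclass correlation and the p<0.10 imbalance cut-off are assumptions, because the documents give none of them.

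- A baseline main effect cancels from a within-person contrast. With complete data the standard error of the 12-month contrast is √(2 × (1 − 0.5) × 2/320) = 0.079, with or without the covariate. The simulated mean was also 0.079. Estimates under never adjusting and always adjusting differed by less than 1e-13, so the rule gives the same result, with power about 0.91 each way. That level reflects complete data and the assumed correlation; it does not restate the trial's power.
- With about 30% lost by month 12, power for always adjusting against the rule was 0.854 and 0.853 (ρ = 0.3), 0.854 and 0.852 (ρ = 0.5), and 0.874 and 0.863 (ρ = 0.65). Type I error differed by no more than 0.002.

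**3. A between-group contrast at 12 months.** In closed form, always adjusting for covariates that explain a share R² of variance gives Φ(2.804/√(1 − R²) − 1.96):

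- R² = 0.10: Φ(2.956 − 1.96) = 0.84
- R² = 0.25: Φ(3.238 − 1.96) = 0.90

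Simulation with six covariates, 224 per arm and 8,000 runs. The rule admits a covariate when its baseline difference has p<0.10. The column headed better of two takes the smaller p-value from the unadjusted and fully adjusted models.

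| R² (assumed) | Type I: never | always | rule | better of two | Power: never | always | rule |
|---|---|---|---|---|---|---|---|
| 0.10 | 0.049 | 0.047 | 0.043 | 0.063 | 0.81 | 0.84 | 0.81 |
| 0.25 | 0.044 | 0.049 | 0.038 | 0.070 | 0.80 | 0.89 | 0.82 |
| 0.50 | 0.052 | 0.049 | 0.030 | 0.084 | 0.80 | 0.98 | 0.84 |

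The Monte Carlo standard error at 5% is √(0.05 × 0.95/8000) = 0.0024, so small differences between type I columns are noise. Unrounded, the rule's loss is 0.840 − 0.812 = 0.03 at R² = 0.10 and 0.894 − 0.817 = 0.08 at R² = 0.25. With one covariate at ρ = 0.5, cut-offs of p<0.05, p<0.10, p<0.20 and a standardised difference above 0.1 gave power 0.82 to 0.85 against 0.90, and type I error 0.035 to 0.041.

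**4. Covariates that enter by time and predict change.** A run with four covariates gave 0.81 (rule) against 0.84 (always) at R² = 0.10, and 0.82 against 0.90 at R² = 0.25. The size of the loss matches step 3.

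**5. Leaving out the ratio.** Assume equal enrolment under each ratio, and 12-month change that differs by δ between 1:1 and 3:1 cohorts, with 2:1 midway.

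- Workshop shares are 1/2, 2/3 and 3/4 (sum 1.917); control shares are 1/2, 1/3 and 1/4 (sum 1.083).
- Mean cohort score (0, ½, 1) in the workshop arm: (0.333 + 0.750)/1.917 = 0.565. In the control arm: (0.167 + 0.250)/1.083 = 0.385.
- Bias in the unadjusted difference: (0.565 − 0.385)δ = 0.18δ. For δ = 1 PHQ-8 point that is 0.18 points, or 0.18/1.5 = 12% of the target difference.

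The documents give no δ, and it may be zero. By the cancellation in step 2, a ratio main effect alone would not remove this bias from the change contrast; ratio has to enter by time.

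**The case against.** The strongest reply is that the named primary test is hardly touched. It is a within-person contrast with baseline among the outcomes, and step 2 shows that main-effect covariates leave it unchanged with complete data and move it by about 1 power point at most with 30% dropout. This stands. A reader might infer from the rule that the primary test loses power or is conservative; the documents do not support either as a general statement. They also do not support a claim that the 0.80 is too high.

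Conservatism is not assured in any case. It follows from selection on imbalance alone, whereas the visual check leaves room for choice, and exploiting that choice moves the error the other way. Nothing in the documents suggests that anyone intends to do so.

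It is also fair to say that adjustment is not wholly driven by imbalance, since the memo fixes ratio. Section 8.26 belongs to an application that still describes 320 per arm, so its silence on ratio is a matter of reconciling two documents.

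Finally, no document shows that age, gender, relationship, ADL need or behavioural symptoms predict PHQ-8 change, and the R² values are assumed. This also stands: the list is for the team to settle, and the power gain may be small.

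Two things limit the reply. Section 8.4 places the main comparison at 12 months, and both power calculations are framed as group comparisons among participants remaining at the end of the study. A between-group reading at 12 months is therefore a live possibility. And whatever the power effect, the rule still does not say which model will be fitted.

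**Conclusion.** The concern holds as a matter of prespecification. The primary model depends on a visual check by arm, selects on imbalance rather than prognosis, and disagrees with the memo about the randomisation ratio.

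- **Planned power:** 0.80 stands.
- **Group-by-time test, main-effect covariates:** practically no effect on power or type I error.
- **Between-group 12-month contrast, or by-time covariates that predict change:** about 3 points lost against always adjusting at R² = 0.10 and 8 points at R² = 0.25, both assumed.
- **Type I error for the 12-month contrast:** 0.043 and 0.038 at those values under selection on imbalance alone; 0.063 to 0.084 over R² 0.10 to 0.50 if the better p-value were taken.
- **Ratio:** illustrative bias of 0.18 times any difference in 12-month change between 1:1 and 3:1 cohorts.

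This should be corrected because it concerns the primary analysis and the correction is cheap. It does not invalidate the design.

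**What to change.** Replace the sentence in section 8.26 with a fixed covariate set, used regardless of balance:

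- randomisation ratio as a categorical term, which brings section 8.26 into line with the memo;
- a short list of prognostic variables already in the baseline survey (section 8.10, item 5a), for example caregiver age, gender, relationship to the person with dementia, care-recipient ADL need and behavioural symptoms.

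State that each term enters with its interaction with time, so that it acts on the 12-month group contrast. Keep the baseline plots as description, and use imbalance-chosen covariates in a sensitivity analysis only.

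The cost is one SAP sentence and no new data, since ratio comes from the randomisation record. The downside is extra parameters. If time has four categories and relationship is coded in two, each of the five example variables takes 1 + 3 = 4 parameters and ratio takes 2 × 4 = 8, or 28 in all, which is modest against 448 expected completers.
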